6.3. Experimental sub-group intervention: Wearable Sub-study (EGw)

Participants randomised to the experimental group will be offered the opportunity to join the wearable sub-sample until the required sample size is reached in each clinical centre. If participants agree, and after specific ICF signature, a second randomisation will take place to determine whether they are assigned to the wearable sub-sample or not. Participants assigned to the wearable sub-sample will be provided with an **Oura ring** of their size, and additional data will be collected from these participants.

A potential issue is that, despite purchasing ring sizes based on the most likely gender- and age-specific measurements of the recruited sample, there may still be instances where suitable sizes are not available for participants willing to join this subsample and assigned to the wearable sub-group. To address the potential unavailability of ring sizes for participants assigned to the wearable sub-group, several measures will be implemented. Firstly, the extra rings will be centrally stored at one clinical centre (i.e., IEO), enabling redistribution to other centres if needed. However, fingers other than the index finger may be used without compromising data collection. Furthermore, if a suitable ring size is unavailable for a participant, the enrolment can proceed with the next eligible participant included in the iBeChange intervention group if willing to and randomised to the wearable sub-group. Lastly, if one centre completes recruitment ahead of others, any surplus rings will be reallocated to centres still actively recruiting participants.

The study will provide clear instructions for device use, offer technical support if needed, and ensure participants are fully informed about data security measures by signing a specific informed consent form. In this pilot study, participants will be able to access the Oura ring app, where the visual progress tracking will be available. This can significantly enhance participant engagement and minimise the risk of non-adherence.

Participants will be enrolled across all three clinical centres involved in the pilot study (i.e., ICO, IEO, and UMFCD). 33% of the intervention group will receive a wearable device, corresponding to approximately 30 participants across all centres (180 participants is the total recruitment of the pilot study, 60 participants per centre).

[figure not shown]
Based on the cancer screening type distribution observed in the pilot study, it is estimated that each clinical centre will have 10 participants with wearable devices, distributed as follows:

Table 8. Estimated recruitment per cancer screening type and clinical centre for the wearable sub-study

Cancer screening type	ICO	IEO	UMFCD
Breast (females)	7	8	7
Lung (males/females)	-	2	-
Colorectal (males/females)	3	-	3
TOTAL	10	10	10

If the ring is not available at the time of recruitment, the following workflow (**Figure 4**) will outline how the situation will be managed. The euro symbol means additional costs will be needed; the clock symbol means additional time, which results in the participants receiving the ring at a later stage.

Figure 4. Logistics workflow for wearable assignment depending on recruitment status and size availability

The intervention for participants assigned to the wearable sub-sample will be the same as in the experimental group, consisting of the behavioural change intervention through the iBeChange platform. Additionally, the Oura Ring will enable continuous and passive health monitoring, allowing accurate health assessments and, at future stages, potential support of the identification of risk factors and their targeting (adjusting the intervention if needed), and potentially encourage proactive behavioural changes by increasing participants' awareness of their health metrics.

6.4. Intervention training and supervision

To ensure standardised intervention across recruitment centres and healthcare professionals for the pilot study, the professional intervention has been written in a specific protocol. Summarised documents with key information will be prepared for health care professionals to review in case of doubt. Moreover, specific training sessions will be scheduled to properly prepare and kick off this multicentre pilot study, reviewing recruitment, platform use, and intervention.

This pilot study will be coordinated by ICO team as the main responsible partner of clinical studies within the iBeChange consortium. Supervision of the pilot study will be ensured by regular meetings of a Trial Supervision Committee (TSC) and through the REDCap Platform. TSC includes partners from all recruitment centres, the technical leaders of the app development (i.e., Eurecat) and statistical partners (i.e., SporeData) of the consortium.

The TSC will meet regularly and according to Pilot timings to review its key aspects: recruitment, allocation, participant retention, data collection, discussion of controversial cases, protocol deviations, and technical issues, if needed.

6.5. Measures to minimise bias: randomisation and blinding

Participants will be randomised into either the control or the iBeChange group, with stratification based on recruitment centre and cancer screening type.

For those in the iBeChange group, participation in the wearable sub-study will be optional. To prevent selection bias, participants who opt in will undergo a second randomisation to determine whether they receive the wearable device or not.

Due to the nature of the intervention—where only the experimental group receives a digital behavioural change program—blinding is not feasible in this pilot study. However, to minimise bias in outcome assessment, all evaluations will be conducted remotely, ensuring that responses from participants in both groups are collected without direct influence from healthcare professionals.

7. Data Flow, management and protection

7.1. Description of Data Processing

This pilot study involves data collection through online questionnaires, via the iBeChange app, and with the use of wearable devices. This section addresses both the Pilot Study and anticipated RCT data flow requirements.

The data will be collected directly from participants in the form of questionnaire response data via REDCap forms. Data will also be collected from recruitment centres, including demographic data. The data items will be held within the REDCap platform hosted by ICO and to be used by all three clinical centres, and within the iBeChange app under development by SIMAVI and Eurecat (technical partners associated within the iBeChange European project consortium). Data collected from participants through the iBeChange app consists of questionnaires and voice recordings (raw data). These data will be collected during the periodic feedback that they will be invited to give, as outlined in Section 7.2 and Section 6. The voice raw data will be stored on Eurecat's server only for participants who provided their consent and managed in compliance with GDPR regulations to ensure data security. Wearable data will be collected through the Oura ring app in participants enrolled in the Wearable sub-study.

Data within the iBeChange platform will be accessed by technical teams within the consortium for the purposes of developing the platform and user interface, assessing and analysing the data for model generation and algorithm training, as well as the impacts and outcomes of the system. Data will be pseudonymised for access by the technical partners. Data will not be shared outside of the platform and REDCap server except for any analysis data used for publication. Access to data may be required by journal editors for results verification but will be limited strictly to what is necessary for their review and will not likely require access to identifiable data for this purpose.

The data collected through the Oura Ring will be stored on Oura's servers, located in Finland (EU), and managed in compliance with GDPR regulations to ensure data security. Data transfer will be explicitly agreed by the participants both in the informed consent and within the app.

Data collected through the Oura Ring will be retrieved from Oura server by using the Oura API and sent to iBeChange server managed by Eurecat. After wearable data have been stored in the iBeChange server, technical partners could access them to (1) compute meaningful indicators from time series (Politecnico di Milano) that will be stored in the iBeChange server, (2) incorporate them in the recommender system (Politecnico di Milano, Eindhoven University of Technology) in order to optimise the timing for sending recommendations.

The aggregated results of the analysis will be available to the Recruitment Centres and to SporeData, the statistical partner of the Consortium, for performing statistical analysis.

Data for the studies will be stored for at least 5 years for archiving purposes in line with regulatory requirements after the end of the pilot study and RCTs. The precise retention periods will be determined by the local jurisdiction's requirements in Italy, Romania and Spain in line with the recruitment centres' national regulations. This will be specified in the Joint Controller Agreement. Data will also be archived and retained under the same terms in the event that a participant withdraws from the Pilot Study or RCT. At the point of withdrawal, the data will be archived, and no further research will be conducted with it and it will be retained in line with national requirements as outlined earlier in this paragraph.

IBeCHANGE ID: 101136840

7.2. Data Processing Particulars and Data Flow Diagrams

7.2.1. Participant Recruitment and Studies Management Stage

[figure not shown]
Please refer to Figure 5 below. The starting point for the data flows is contained within the Participant Recruitment and Study Management Phase and commences when the Health Care Professional (HCP) at each of the recruitment centres (ICO, IEO and UMFCD) approaches a patient during routine care/cancer screening and asks whether they would like to Participate in the iBeChange Study. The Patient will either consent as per steps 0C or decline as per steps 0D. On declining, that patient will no longer engage with iBeChange. Note that the steps listed in this section refer to each of the participating centres (ICO, IEO and UMFCD).

On consenting, the patient will become a Participant and will be randomised to be part of the Control Group at steps OCC or the Experimental Group at steps OCE. If randomised to the Experimental Group, Participants will be asked if they agree to being part of the wearables study, at which point they will be further randomised under steps 0CW to see if they form part of the Wearables sub-study. At steps 0CV, participants will also be asked if they consent to doing voice recordings for the voice recordings analysis and have the risks involved with this explained to them as part of the consenting process. These steps are also represented in the iBeChange pilot study diagram in Figure 1.

Their HCP will register each participant under the steps 1HCR according to the Group they are randomised to and whether they will form part of the Wearables sub-study and whether they have consented to voice analysis. The information will be gathered locally via the REDCap System available at each site and hosted by ICO as per steps 1HCR. The REDCap system has several functions where one is for HCPs to complete information entry.

Figure 5. Data Flow Diagram: Data processing for the iBeChange pilot study (next page)

Deliverable 5.1 iBeChange pilot study protocol

IBeCHANGE ID: 101136840

REDCap will also manage study data and identifiable participant data and will also randomise participants. REDCap will also manage participant questionnaire responses which the participants in both control and experimental Groups will use. The data collected will be as per the REDCap Specification available in the iBeChange_variables_REDCap_20Mar25.doc. At the point of recruitment, a file will be opened on REDCap for each participant and a Study ID will be assigned (acting as the project PseudoID). Participants in the Control Group will fill out questionnaires at the outset and at 12 weeks into the pilot study (end of the intervention) as per steps 1CCQ. The Experimental Group will be asked to also complete questionnaires at the start and at the end of the study (additionally assessing satisfaction and usability of platform and smart rings use) as per steps 1PR.

If a Participant has been registered in the Wearables sub-study they will need to register for an Oura Ring Account on the Oura Servers that are not controlled by any iBeChange Partner as per steps 10RU. This will be an arrangement between the participant and Oura directly, where Oura will be a controller of Personal Data in their own right as per their service agreement with the Participant. This will be explained to the Participants when approached to indicate their willingness to join the Wearables sub-study. Data will include a Username, an email account, and a Password, plus the processing of the wearables data as outlined in this protocol's section 3.6.

7.2.2. Platform Use Stage

As the pilot study continues, the Platform Use Stage commences with the HCPs at each site updating data on the PoC tool hosted by Eurecat on the Platform as per the steps 2HPoC. This involves registering the Participant on the PoC tool. It should be noted that at this stage, data will be identifiable, especially if voice recordings are uploaded via the iBeChange app. The data is collected and transferred to the Eurecat Platform in a Pseudonymised form using the Study ID assigned to each participant, with all identifiers taken out of the records submitted from REDCap, as per Step 2HPoC in the DFD. For the Pilot Study, this will be done manually from REDCap by the HCPs at each site, but the aim is to do this automatically for the RCT.

The Platform will host the Participant App and PoC system. This stage of the studies also relates to the data gathering from the participants via the Experimental Group App as per Steps 3PAA in Figure 5. Participants will be encouraged to use the App to add data, including voice recordings for emotion/stress analysis.

[figure not shown]
The Wearables data in the first instance via the Oura Ring via the Experimental Group app once the HCP has connected their accounts will also be uploaded to the Eurecat Platform. The Oura app will be automatically connected to the Platform through the app, redirecting to Oura server once the user account is already activated. The Oura Ring will also upload data to the Platform automatically under steps 3ORA for the RCT as per steps 3ORRC. Wearable data stored in the Oura server will be transferred periodically (ideally, at least once a day) through Rest API to the Eurecat's Platform (step 3ORA).

Voice recordings for the emotional/stress analysis will also be added via the App where Participants have consented to do so. Please see the Oura Ring Logistics Flow Diagram at Figure 4 and the App Specification Data Flow Diagram for the full details of data processing. The details of data collected are available at sections 4.3, 4.4 and 4.5.

Note that Figure 6, on the next page, outlines all steps to this point in more detail.

Figure 6. Participant recruitment and data flow diagram (next page)

Deliverable 5.1 iBeChange pilot study protocol

7.2.3. Analysis Stage

Within the Analysis Stage, there are several points. SIMAVI will develop the app interface tool as per step 4DA and will need to process data on the platform to assist in their development and deployment. POLIMI will access the platform-held data as per step 5PZ and as described in Section 7.1. Within POLIMI, there are two groups, one focusing on wearables and the intervention wearables, where they need all the wearable data and the interventional/clinical data for correlation analysis. Another group will be running reinforced learning and will only require interventional/clinical data.

8. Statistics

8.1. Statistical hypotheses

The pilot study aims to assess the feasibility of a future larger RCT. It will also inform RCT planning, define the study protocol, and optimise the IBeChange intervention and study design.

Therefore, the statistical focus is on feasibility-related outcomes rather than formal hypothesis testing for clinical efficacy. The feasibility of the future RCT will be evaluated based on key metrics, including recruitment rates, completion rates, data completeness, and participant/staff feedback. The following feasibility hypotheses will guide our assessment

1. Recruitment Feasibility Hypotheses

- a. H₀ (Null Hypothesis): The recruitment rate will be insufficient for a future RCT, with an estimated rate below the predefined feasibility threshold (50% of eligible patients consent to participate).
- b. H₁ (Alternative Hypothesis): The recruitment rate will meet or exceed the feasibility threshold, indicating that the trial can recruit participants at an acceptable rate for an RCT.

2. Data Collection Feasibility Hypotheses

- a. Ho: The case report form (CRF) completion rate will be suboptimal, with excessive missing data (>10% missingness in primary outcomes).
- b. H₁: The CRF completion rate will be adequate, with minimal missing data, indicating good feasibility of data collection.
- 3. Acceptability and Usability Hypotheses
 - a. H₀: Participants will report low usability and satisfaction scores, assessed through the one single 0-10 visual analogue scale item per construct (mean score < 7)
 - b. H₁: Participants will report acceptable usability and satisfaction.
- 4. Operational Feasibility Hypotheses
 - a. Ho: The time required to complete each trial step (e.g., participant recruitment, data entry, and data transfer) will exceed the predefined thresholds (recruit 100% of participants within the first 3 months and complete data entry and transfer within 1 month of the end of the pilot).
 - b. H₁: The time required to complete each trial step will be within planned limits, supporting the feasibility of the future RCT.
- 5. Wearable usage Hypotheses
 - a. H₀: Participants in the wearable sub-group will not consistently use the wearable device, with fewer than 80% of participants using the device at least 4 days per week.
 - b. H₁: Participants in the wearable sub-group will consistently use the wearable device throughout the study.

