5.2. Strategies for recruitment and retention

Three recruitment centres are participating in iBeChange. These are:

Table 6. Recruitment centres: characteristics and expected recruitment size for the iBeChange Pilot Study

Centre	City, Country	Ownership	Funding Type	Type of entity	N per cancer type (expected)
Institut Català d'Oncologia (ICO)	Hospitalet del Llobregat, Spain	Public	Catalan Health Service (CatSalut)	Hospital and comprehensive cancer centre integrated into the Catalan public health system	Breast = 20 Colorectal = 40
Istituto Europeo di Oncologia (IEO)	Milano, Italy	Private, Non- Profit	Private funding, with agreements for public healthcare services	Hospital and comprehensive cancer centre that collaborates with the Italian National Health Service for some publicly funded treatments	Lung = 10 Breast = 50
University of Medicine and Pharmacy Carol Davila (UMFCD)	Bucuresti, Romania	Public	Publicly funded as a state university hospital	General hospital ascribed to public university receiving funding through the Romanian Ministry of Education and Ministry of Health	Breast = 20 Colorectal = 40

Given their different nature, the recruitment strategy will be slightly different in each recruitment centre:

ICO, Spain (breast and colorectal)

Breast cancer:

Participants at ICO are recruited through the breast cancer screening program. Through a postal letter, women at **50-70** years old are invited to the program. Only those women attending a mammography test at ICO's radiology service are suitable for participation. Mammography technicians provide a brochure with a Quick Response (QR) code/phone to contact to chat.

Participants access a webpage with basic study information, where they can either directly contact the study personnel or provide their contact details and consent to be contacted. If they agree, participants will be contacted by telephone by a researcher to provide more information. If inclusion/exclusion criteria and willingness to participate are confirmed, then an in-person appointment for ICF signature is scheduled.

Colorectal cancer:

Participants at ICO are recruited through the colorectal cancer screening program. Through a postal letter, individuals at **50-70** years old are invited to the program. Only those individuals returning a faecal occult blood test (FOBT) sample to the pharmacies are suitable for participation. Pharmacies' personnel provide a brochure with a QR code/phone to contact to chat.

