Participants access a webpage with basic study information, where they can either directly contact the study personnel or provide their contact details and consent to be contacted. If they agree, participants will be contacted by telephone by a researcher to provide more information. If inclusion/exclusion criteria and willingness to participate are confirmed, then an in-person appointment for ICF signature is scheduled.

IEO, Italy (breast and lung):

Breast cancer:

At IEO, women **aged 45-69** years old can participate in breast cancer screening by voluntarily booking, both privately and via national health care system. They are contacted by phone call to be introduced to the iBeChange study.

Interested people will receive via email an informative brochure with a study overview and a link directing to the project's website.

Signed informed consent will be collected at the cancer screening test appointment.

Lung cancer:

At IEO, individuals **aged 50-80** years with no clear signs of lung cancer (e.g., worsening cough, haemoptysis, unexplained weight loss) who are current smokers or former smokers that quit less than 15 years ago are eligible to participate in lung cancer screening by voluntarily booking if they have smoked at least (a) 10 cigarettes per day for 30 years, (b) 15 cigarettes per day for 25 years, or (c) 20 cigarettes per day for 20 years (> 20 packs/year). Individuals with history of cancer in the past 5 years are excluded. Since lung cancer screening is not usually available at IEO and is not offered by the Italian health care system, an *ad hoc* lung cancer screening program will be organised and promoted for this pilot study. Eligible participants will be able to access the screening with no additional costs. They are contacted by phone call to be introduced to the iBeChange study.

Interested people will receive via email an informative brochure with a study overview and a link directing to the project's website.

Signed informed consent will be collected at the cancer screening test appointment.

UMFCD, Romania (breast and colorectal):

Breast cancer:

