8.2. Sample size determination

The sample size for the pilot study was determined as 10% of the total sample for the full RCT, which covers its feasibility nature. For the full RCT, assuming a 60% refusal rate, a significance level of 0.05, and a 5% difference between groups, a sample size of 900 participants per group would result in a power of 80%. Therefore, the estimated sample size for the pilot was 180 participants (90 per group).

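### The recruitment criterion (50% of eligible people consenting) sits above the 40% consent implied by the RCT's own 60% refusal assumption, and the denominator of the 60% is not stated

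*Protocol*

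**What the plan says.** Section 8.1 of the Protocol lists five feasibility hypotheses that are to guide the assessment. The first concerns recruitment. Its null is that recruitment will not suffice for the later RCT, "with an estimated rate below the predefined feasibility threshold (50% of eligible patients consent to participate"). Its alternative reads: "The recruitment rate will meet or exceed the feasibility threshold, indicating that the trial can recruit participants at an acceptable rate for an RCT".

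Section 8.2 sizes that RCT: "For the full RCT, assuming a 60% refusal rate, a significance level of 0.05, and a 5% difference between groups", with 900 participants per group and 80% power. The pilot is 10% of the RCT, which gives 180 participants (90 per group).

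Section 8.4 confirms that the share of eligible people who consent is what will be measured. Table 3 asks for recruitment number and rate by centre and overall.

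Section 5.2 describes different routes into the study:

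- **ICO:** mammography technicians or pharmacy staff "provide a brochure with a QR code/phone to contact to chat". Eligibility and willingness are confirmed only in a later telephone call, to people who made contact or left their details.
- **IEO:** the wording is "They are contacted by phone call to be introduced to the iBeChange study".
- **UMFCD:** general practitioners check criteria and willingness at a visit.

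**The concern.** Sections 8.1 and 8.2 stand next to each other and concern the same future RCT. One sets the consent rate below which recruitment is judged inadequate. The other gives the refusal rate on which the RCT is planned. On the ordinary meaning of refusal, the planning rate lies below the bar. No text explains why the pilot must do better than the RCT's own assumption, and the pilot has no separate consent assumption.

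Recruitment is part of the primary feasibility endpoint. As written, the criterion can come out negative when the RCT's assumption has been met. That would leave the team to decide, after seeing the data, which of the two figures it had meant.

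The differing routes add to the difficulty. At ICO a person who ignores the brochure is, on the described workflow, never assessed for eligibility. A consent rate among eligible people therefore does not measure the same thing there as at a centre that telephones people.

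**Working it through.** **Inputs**

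- Threshold: 50% of eligible people consent (8.1).
- Planned refusal: 60% (8.2), denominator not stated.
- Pilot size: 180. RCT size: 2 × 900 = 1,800 (8.2).
- Measured quantity: consenting / eligible (8.4).

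**The plan's own figures**

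Pilot: 0.10 × 1,800 = 180, which reproduces.

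The 900 per group cannot be checked from the stated inputs, because endpoint, base rate and sidedness are not given with "a significance level of 0.05" and "a 5% difference between groups". Under assumed base rates (two-sided, 80% power, no continuity correction), a five-point difference needs:

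| Assumed rates | n per group |
|---|---|
| 5% vs 10% | 435 |
| 15% vs 20% | 906 (power at 900 = 79.8%) |
| 47.5% vs 52.5% | 1,569 |

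So 900 can be reached without using the refusal rate. Nothing below depends on it, apart from the RCT workload at the end.

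**Step 1: the two rates.** If refusal is counted among eligible people asked, implied consent = 1 − 0.60 = 0.40, which is below 0.50.

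**Step 2: people needed for the pilot.** At 40%: 180 / 0.40 = 450 eligible. At 50%: 180 / 0.50 = 360 eligible.

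**Step 3: chance of meeting the 50% rule.** The design fixes the number enrolled. The observed rate is therefore at least 50% only if the 180th consent comes within 360 eligible people, that is, with at most 180 refusals (negative binomial).

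| True consent | P(observed ≥ 50%), enrolling until 180 consent |
|---|---|
| 40% | 0.000077 (about 8 in 100,000) |
| 45% | 0.032 |
| 50% | 0.52 |

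If instead exactly 450 eligible people were asked, P(Bin(450, 0.40) ≥ 225) = 0.000011. That is smaller still, but it does not match a design that stops at 180 enrolled.

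**Step 4: when would the figures agree?** Suppose 60% is refusal over all people approached, and a share e of them is eligible. Consent among the eligible is then 0.40 / e:

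| e | Consent among eligible |
|---|---|
| 1.0 | 40% |
| 0.9 | 44% |
| 0.8 | 50% |
| 0.7 | 57% |

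They agree only for e ≤ 0.80. The protocol states neither this denominator nor a value of e.

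**Step 5: where could a cut-off sit if 40% is the plan?** With 450 eligible people and true consent of 40%:

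- Cut-off 40%: P(Bin(450, 0.40) ≥ 180) = 0.52.
- Cut-off 35% (0.35 × 450 = 157.5, so 158): P(Bin(450, 0.40) ≥ 158) = 0.985. Enrolling until 180 consent (at most 514 eligible, since 180 / 514 = 35.02%) gives 0.991. Either way it is about 99%.
- If true consent is only 30%, the 35% cut-off is met about 1% of the time (0.011 and 0.008).

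**RCT workload.** 1,800 / 0.40 = 4,500 eligible people, against 1,800 / 0.50 = 3,600.

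**The case against.** Four points can be made for the plan.

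- **The two rates may have different denominators.** Section 8.1 speaks of eligible patients. Section 8.2 does not say who the 60% is counted over, and section 7.2.1 describes people who are approached and then consent or decline. A reader might infer that the two figures cannot both hold. The documents do not support that: step 4 shows they can, for e ≤ 0.80. What can be shown is an unexplained gap and an unstated denominator.
- **The 60% is given for the RCT, not the pilot.** This is true. Carrying it over is an inference, though a reasonable one: the pilot is sized as a tenth of that RCT and has no rate of its own.
- **Missing the threshold stops nothing.** A reader might infer that a pilot at 40% would be declared infeasible or end in a no-go. The protocol does not say so. Recruitment is one of five hypotheses that guide the judgement, no overall rule is stated, and section 5.3 foresees adjustments for the RCT. This objection stands and limits the point to one criterion.
- **Centre differences are partly handled.** Section 5.2 acknowledges them and Table 3 asks for rates by centre. A reader might infer that ICO volunteers would lift a pooled rate over 50%. Suppose 60 are enrolled per centre, with 40% consent at IEO and UMFCD (150 eligible each) and an assumed 90% to 100% at ICO (67 to 60 eligible). The pooled rate is then 180/367 to 180/360, or 49% to 50%. It reaches the bar only at the extreme, or if the other centres exceed 40%. The case for reporting by centre remains.

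**Conclusion.** The point holds in a limited form. On the ordinary reading, the recruitment criterion is ten percentage points stricter than the RCT's planning assumption, and nothing in the protocol reconciles the two. If true consent among eligible people in the pilot is 40%, the recruitment hypothesis falls under its null with near certainty.

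This rests on two assumptions: that the 60% is refusal among eligible people asked, and that the RCT's rate carries over to the pilot. If refusal is counted over everyone approached and no more than four in five are eligible, the conflict disappears, but the protocol would have to say so.

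The defect is one of consistency in a decision threshold. It does not touch the pilot's 180, the allocation or the effect analyses, and it does not amount to stopping the programme. It should still be corrected, because it governs how part of a primary endpoint is read and choosing between 40% and 50% afterwards would be post hoc.

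**What to change.** Before any recruitment data are seen, state one consent assumption with one denominator, consent among people confirmed eligible, in both 8.1 and 8.2. There are two ways to do it:

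1. Restate 8.2 with 50% refusal. The cut-off then equals the plan, so a pilot exactly on plan would pass only about 52% of the time. The text should acknowledge this.
2. Base 8.1 on the planned 40%. Set the cut-off for inadequate recruitment somewhat below it, for example 35%, which a true 40% rate would meet about 99% of the time with 450 eligible people. Keep 50% as the level for proceeding unchanged. A bare 40% cut-off would pass only about 52% of the time at a true 40%.

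Report the consent rate per centre, with a note that at ICO eligibility is checked only after self-referral. Do not apply the threshold to brochures handed out: that population includes people never assessed for eligibility, and counting it would need tallies from technicians and pharmacy staff outside the study team.

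The cost is a few sentences in 8.1 and 8.2, and a log at each centre of people confirmed eligible and people consenting, which the rate in 8.4 already requires. The pilot's sample size does not change.
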